2. ASSESSMENT AND MANAGEMENT OF RISK

With respect to the safety and wellbeing of participants, before the start of the study, approval will be sought for the study protocol, informed consent forms and other documents from an NHS research ethics committee (REC) and the Health Research Authority in the UK. The intervention provided will be therapist-supported digitally delivered cognitive-behavioural therapy. There are few potential risks to participants. In general, this psychological intervention, when delivered appropriately, is unlikely to

be harmful to participants, and is relatively safe, with no unexpected side effects, although a small percentage of patients can deteriorate during psychological interventions. This is a NICE recommended therapy. There are considerable potential benefits from receiving RF-CBT as it is proven on average to reduce worry, rumination, anxiety and depression. The risk is no more than normal standard practice with digital CBT routinely provided in the NHS.

There is no known health risk associated with any of the assessments or interventions proposed. We anticipate that the supported digital CBT will on average improve wellbeing and reduce symptoms. Nonetheless, we will assess for potential harms. The research team will be provided with a standard operating procedure and trained to assess and manage risk in order to safeguard participants, including referral to local treatment services, and access to a designated clinician to support them.

The initial screening process for the study will exclude anyone reporting current or past severe psychiatric disorder (current or past diagnosis or treatment for psychosis or bipolar disorder; current severe PTSD or alcohol/substance abuse or dependence) and those reporting elevated suicidality (scoring 1 or more on item 9 of the PHQ-9 and then answering yes to automated follow-up questions asking about plans or intentions regarding suicide). The screening tool will automatically signpost these individuals towards appropriate guidance and help, including general information on the presenting symptom, recommended actions to keep themselves safe, advice to seek medical help from their GP or relevant local clinician/service and direct links to relevant national sources of help. The form will enable the person to volunteer their contact details and GP details if they would like to receive a phone call from a member of the research team, and potentially be referred to their GP. Excluded individuals will still be able to access other treatment outside the study.

Participants who report risk (e.g. suicidal thoughts) or significant worsening symptoms on the follow-up assessments or during contacts with PWPs will also receive automated messaging recommending actions and signposting. Significant worsening symptoms is defined as a deterioration of movement across two or more score categories on the GAD7 or PHQ-9 from baseline to 16-weeks or from baseline to 52-weeks follow-up. At the point of automated signposting, participants can request contact from a study PWP or contact a study PWP via e-mail or telephone to seek advice. PWPs will follow standard risk management protocols that include contacting the individual, assessing their situation and status (e.g., standardised checklist concerning suicidal or self-harm thoughts, plans, intentions, preparation, barriers, and safety measures), providing safeguarding, safety plans and guidance, and, as necessary, referring to relevant clinical services, including contacting participants GP, crisis teams, or acute emergency services as necessary. This procedure has been successfully used in prior trials which received ethical approval including both local institutional approval and NHS approval.

Similar standard operating procedures including risk assessment, signposting to relevant sources of help and bringing in relevant clinically qualified members of the team (clinical psychologists, psychological wellbeing practitioners in UK), will be used by research staff if participants report worsening of symptoms or suicidality during interviews or contacts with research staff.

The study has been designed in collaboration with a Lived Experience Advisory Panel (LEAP) who have advised on all aspects of the intervention.

A detailed risk assessment has been completed by Exeter Clinical Trials Unit and will be maintained throughout the study.

Information about possible benefits and risks of participation will be described in the Participant Information Sheet (PIS).

USA-specific detail

The study will be reviewed and approved by an Institutional Review Board at UCLA, USA.

Digital CBT is widely available for patients and is frequently incorporated into research studies in the USA.

Coaches, supervised by a licensed clinician, will support participants recruited in the USA.

For participants recruited in the USA, automated signposting to support services will be tailored to services specific to the local study population in the USA. USA-based participants will be students at the Imperial Valley Community College (IVC), so services will include the student support services already available through the College.

During screening, if individuals indicate the exclusion criteria of active suicidality, severe PTSD or diagnosis of bipolar disorder, substance abuse or psychosis they will be provided with contact information for the college health centre counselling services, as well as community emergency resources.

If, during the study, participants indicate suicidality on self-report assessments, they will be provided with information about community and emergency resources. Additionally, study staff may provide participant contact information to the IVC Behavioral Intervention Team (BIT) for their team to conduct independent follow up with students. Participants will be informed of this potential for information sharing in the informed consent signed before study enrollment.

If a participant discloses suicidality during an encounter with study staff, study staff will provide the participant with information about community and emergency resources, and report to the Coaching Supervisor. Additionally, study staff may provide participant contact information to the IVC Behavioral Intervention Team (BIT) for their team to conduct independent follow up with students.

If during the course of the study a participant's responses to surveys indicate a significant worsening of symptoms, they will be provided with contact information for the IVC health center, as well as community and emergency resources. This is defined as a deterioration of movement across two or more score categories on the GAD7 or PHQ-9 from baseline to 16-weeks or from baseline to 52-weeks follow-up.

3. OBJECTIVES AND OUTCOME MEASURES / ENDPOINTS

We aim to better understand the mechanisms and active treatment components that underpin the effective reduction of RNT (e.g., worry, rumination), a proven major active ingredient and mediator in the treatment of anxiety and depression.

3.1. Primary objectives

The objective of this study is to delineate the causal mechanisms underpinning reduction in RNT, a characteristic of the most common mental health conditions. Our specific inter-related research questions are:

(a) What are the causal mechanisms that underpin effective cognitive-behavioural interventions to reduce RNT?

(b) What are the active ingredients within RNT-focused cognitive-behavioural therapy (RF-CBT) that effectively manipulate these mechanisms, and, thereby, reduce RNT?

3.2. Secondary objectives

Secondary objectives are to:

1. To compare the changes in anxiety and depression symptoms in participants across the treatment period with respect to the main effect of each treatment component and their interactions
2. To compare the changes in diagnostic status in participants across the treatment period with respect to the main effect of each treatment component and their interactions
3. Examine potential moderators of treatment outcome by condition and to examine potential personalisation.

Exploratory analyses will consider how different contexts (baseline characteristics, e.g., country, socioeconomic status, level of current symptoms) have an impact on the efficacy of targeting RNT and the efficacy of the specific components (active ingredients) and seek to identify markers that can predict whether an individual will respond to each of the specific component factors within the intervention. These potential markers include baseline assessment and EMA. Critically, and uniquely, this design affords us data that can be used to develop personalized treatment matching not between different treatments but rather to select and match the relevant components within a treatment approach (e.g., identifying who may benefit most from targeting RNT-as-a-habit versus increased self-compassion), with transformative potential for individualising treatment and, thereby, improving outcomes. There is emerging evidence that matching treatment correctly to the individual can significantly improve outcomes. As an exploratory first step, we will test which pre-treatment measures moderate the differential effects of each factor.

Because individual predictors are usually weak and underpowered, an improved approach is to use composite models that combine individual moderators to produce Individualised Treatment Rules (ITRs) that can guide the selection of active ingredients (components) most likely to be helpful for each individual. Machine learning approaches have been validated as a means to develop effective composite models. It has been estimated that between n=350-500 patients per arm is estimated to be sufficient to provide stable estimates of ITRs. As such, the factorial trial will be sufficiently powered to examine potential ITRs for each main factor, enabling the identification of rules to predict who will benefit most from which treatment component, which has the potential to transform intervention efficacy. Identifying ITRs is a key step towards precision treatment personalisation and to prepare for definitive future trials that test whether treatment allocation using ITRs improves outcomes relative to random allocation or usual clinical practice. In addition, a potential benefit of using a digital intervention coupled with EMA is that if successful prediction models that utilise EMA can be derived and tested, the efficacy of the open access digital therapy intervention for RNT could be further enhanced by accompanying it with EMA apps that support ongoing selection of the intervention components most likely to be effective for a given individual.

Baseline measures will include those that have predicted treatment outcome in prior studies: demographics, symptoms, stress, personality, cognitive measures. For example, theories of RNT predict that levels of executive functioning would moderate ability to switch processing style and break RNT-as-a-habit, and that histories of chronic stress or early adverse events would moderate breaking RNT-as-a-habit. We will also have ecological momentary assessment (EMA)^{1,2}, providing detailed contextual information on patterns in the relationships between mood, RNT, and daily behaviour.

These data open the opportunity for future analyses to examine possible moderators of response to specific components within RF-CBT and to develop individualised treatment rules (e.g., via machine learning methods) that can predict which components an individual should receive. Because there may be considerable individual differences in response to each treatment component, knowing who responds optimally to which treatment component may enable us to personalize within the treatment package and, thereby, transform treatment outcomes.

4. Examine the mechanism and factors related to implementation

To inform understanding of mechanisms and barriers and facilitators of sustained implementation within a mixed model approach, semi-structured online or telephone interviews will be conducted with 30 UK trial participants at 16 weeks and 12 months, matching quantitative data collection points. Qualitative data will be analysed using realist-informed thematic analysis, with NVivo v14, to deductively investigate each of these areas but we will also include an inductive approach to identify any novel findings. See Section 11 Process Evaluation for details.

5. Development and examination of linguistic Natural Language Processing markers

The study will include collection of text material from participants both within baseline and follow-up assessments (tasks to describe problems and concerns) and during the online intervention package. This material will be analyzed for linguistic markers of changes in relevant mechanisms (e.g., specific versus abstract descriptions of events, more self-critical versus more self-compassionate language) using establishing linguistic feature analysis and the use of machine learning and AI to train and test models. We will explore whether these markers can be provided in real-time in order to provide ongoing feedback to participants within the intervention to support their learning of skills.

3.3. Outcome measures

3.3.1. Primary outcome

The primary outcome will be change in RNT as indexed by the Perseverative Thinking questionnaire³⁶ from baseline to post-treatment (16 weeks) as recommended in the Wellcome Review of Active Ingredients section on RNT⁸.

3.3.2. Secondary outcomes

The following secondary outcomes will be measured using standardised validated measures at baseline, and post-treatment at 16 weeks and 52 weeks post-randomisation via participant survey on REDCap:

1. Change in anxiety measured with GAD-7³⁷
2. Change in depression measured with PHQ-9³⁸
3. Change in mental wellbeing measured with WEMWBS (Warwick-Edinburgh Mental Wellbeing Scale short-form³⁹)
4. Change in levels of rumination measured with RRS-Brooding subscale⁴⁰
5. Change in levels of worry measured with PSWQ (Penn State Worry Questionnaire short-form)⁴¹
6. Change in social functioning measured with WSAS (Work and Social Adjustment Scale)⁴²

The following secondary outcome will only be measured at baseline and at 16 weeks post-randomisation (captured by the mPath app):

7. Change in RNT in everyday life measured with EMA¹ (aggregate person-level ratings of RNT across 10 day period; variability of RNT; relationship of RNT to mood state & contextual events; automaticity of RNT, based on EMA items). This provides an ecologically valid measure, in the real-world, of extent of RNT and how it changes pre-to-post intervention.

We will also assess incidence of major depressive episodes and generalized anxiety disorder across the 12-month follow-up using standardized structured online measures (adapted Lifetime history of depression and anxiety disorders (adapted LIDAS)⁴³ for depression, adapted GAD for anxiety (based on Roemer et al., 1995⁴⁴) enabling us to test which factors have long-term effects on RNT and on the prevention of first incidence or recurrence of episodes of depression and anxiety, providing direct data to inform transformation of early interventions.

3.3.3. Process measures (putative mediators)

A series of measures will be used to ascertain potential change in the hypothesised mechanisms of interest (abstract to specific concrete processing; self-criticism to self-compassion; increased present moment focus; breaking the RNT habit).

These measures will include:

- Self-report standardised questionnaire measures completed at baseline, 16 weeks, and 12 months (see Table 3 for full details). These include (with associated mechanism in parentheses):
 - Overgeneralisation subscale of Attitudes towards self-scale^{45,46} (abstract to concrete processing)
 - Self-criticism subscale of Attitudes towards self-scale^{45,46} (self-criticism)
 - Adapted self-report habit index⁴⁷ (breaking the RNT habit)
 - Self-compassion scale short-form⁴⁸ (self-compassion)
 - Problem clarification, self-efficacy/mastery subscales from Bern post session report^{49,50} (to assess insight and understanding and general sense of control)
 - 5 facet Mindfulness Questionnaire (short form, 2 subscales to assess present-moment focus)⁵¹
 - Flow Proneness Questionnaire⁵² (leisure only subscale to assess present moment focus)
- Specific analysis of the EMA data – for example to examine the change in level of RNT; the extent to which RNT is associated with low mood (index of habit), the extent of present moment focus in EMA; the extent to which RNT is associated with particular situations or cues (index of habit).
- Micro-assessments during the intervention period providing very brief, repeated measures of putative mediators, taking 2-item versions of measures above. These repeated frequent measurements will enable us to assess changes in putative mediators across time enabling factorial mediation analysis with temporal precedence and to determine if treatment components impact one or more mechanisms, and which change in putative mechanisms is associated with active components and mediates improvement in RNT.

- Linguistic analysis of instructed writing tasks (e.g., asking participants to describe a problem; describe an example of RNT) at baseline and 16 weeks follow-up. Such linguistic analysis enables measurement of how abstract or specific text is, how positive or negative text is, how self-related and repetitive text is, thus providing a behavioural index of the mechanisms of self-compassion and level of processing (abstract vs concrete). Linguistic analysis of text provided by participants will include manual coding for level of abstraction, and the use of well-established vocabulary dictionaries (e.g., Linguistic Inquiry and Word Count software) that can generate counts of particular word categories (e.g., first-person singular pronouns to assess the self-referential thinking associated with rumination; proportion of positive versus negative emotion words to capture shift away from negative evaluation; proportion of abstract versus concrete nouns and verbs as determined from normative linguistic measures), successfully used in our prior research. Building on these established approaches, we will explore automated evaluation of these dimensions using Natural Language processing models (e.g. BERT sentiment decoders, LLAMA) trained to predict the above dimensions in a corpus of text. If viable, we will apply this linguistic analysis to the text provided within the exercises and open text boxes in the treatment platform, which may enable us to gain further insight into therapeutic process, track session-by-session change in these indices and test if these linguistic indices predict outcomes.
- Linguistic analysis of text generated during the intervention – as above

3.3.4. *Exploratory analysis*

There are no exploratory outcomes. As noted above, there will be exploratory analyses of moderators of effects of outcomes – see secondary objectives.

3.3.5. *Table of objectives and outcomes*

Table 1: Table of objectives and outcomes

Objectives	Outcome Measures	Timepoint(s) of evaluation of this outcome measure

Primary Objective: To delineate the causal mechanisms underpinning reduction in RNT, a characteristic of the most common mental health conditions.
 
Our specific inter-related research questions are:
 
(a) What are the causal mechanisms that underpin effective cognitive-behavioural interventions to reduce RNT?
 
(b) What are the active ingredients within RNT-focused
	
Primary outcome: Change in RNT as indexed by the Perseverative Thinking Questionnaire³⁶ from baseline to post-treatment (16 weeks).
 
Secondary outcomes: Change in levels of rumination measured with RRS-Brooding⁴⁰ subscale.
	
 - Baseline - 16 weeks post-randomisation - 52 weeks post-randomisation 
 - Baseline - 16 weeks post-randomisation - 52 weeks post-randomisation

cognitive-behavioural therapy (RF-CBT) that effectively manipulate these mechanisms, and, thereby, reduce RNT? This includes comparing the effects on proposed mechanisms across the treatment period with respect to the main effect of each treatment component and their interactions.
	
Change in levels of worry measured with PSWQ (Penn State Worry Questionnaire – short-form)⁴¹. Change in RNT in everyday life measured with EMA. Process-mechanisms will be assessed by change in:
 
 - Overgeneralisation subscale of Attitudes towards self-scale (abstract to concrete processing)^{45,46}; - Self-criticism subscale of Attitudes towards self-scale (self-criticism)^{45,46}; - Adapted self-report habit index (breaking the RNT habit)⁴⁷; - Self-compassion scale short-form (self-compassion)⁴⁸; - Problem clarification, self-efficacy/mastery subscales from Bern post session report^{49,50}; - 5 facet Mindfulness Questionnaire (short form, 2 subscales to assess present-moment focus)⁵¹; - Flow Proneness Questionnaire (leisure only subscale to assess present moment focus)⁵²; - Brief micro-assessments during therapy course. 	
 - Baseline - 16 weeks post-randomisation - 52 weeks post-randomisation - Baseline - 16 weeks post-randomisation - Baseline - 16 weeks post-randomisation

Secondary Objectives
		


To compare the changes in anxiety and depression symptoms in participants across the treatment period with respect to the main effect of each treatment component and their interactions
	
Secondary outcomes: Change in anxiety measured with GAD-7³⁷ Change in depression measured with PHQ-9³⁸ Change in mental wellbeing measured with WEMWBS³⁹ Change in social functioning measured with WSAS⁴²
	
 - Baseline - 16 weeks post-randomisation - 52 weeks post-randomisation

To compare the changes in diagnostic status in participants across the treatment period with respect to the main effect of each treatment component and their interactions
	
Secondary outcomes: Incidence of major depressive episodes and generalized anxiety disorder using adapted LIDAS⁴³ for depression and adapted GAD⁴⁴ for anxiety.
	
 - Baseline - 16 weeks post-randomisation - 52 weeks post-randomisation

Examine potential moderators of treatment outcome by condition and to examine potential personalisation.
	
As primary and secondary outcomes above.
	
 - Baseline - 16 weeks post-randomisation - 52 weeks post-randomisation

Examine the mechanism and factors related to implementation.
	
Process evaluation semi-structured interviews.
	
 - 16 weeks post-randomisation - 52 weeks post-randomisation

Development and examination of linguistic Natural Language Processing markers.
	
Use of text material from participants, coding and analysed for linguistic markers of mechanisms of interest.
	
 - Baseline - 16 weeks post-randomisation

Refer also to the tabulated schedule of assessments (Section 8).

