1. Shifting from unhelpful abstract to helpful concrete processing style, with evidence that manipulating processing style improves problem-solving and reduces emotional reactivity^{15,25,26}, and training concrete thinking alone reduces RNT^{27,28} (corresponding component/active ingredient in RF-CBT is *increasing specific contextualised detail in description of events and plans*).

2. Breaking RNT-as-a-habit by establishing new, more adaptive habits, with evidence that RNT is a habit^{29,30} and learning new habits reduces RNT^{28,31} (corresponding component(s) in RF-CBT: *identify warning signs, stimulus control, implementation intentions, repeatedly practise alternative strategies*).
3. Replacing self-criticism with self-compassion, identified as a potential active ingredient⁸ (corresponding component(s) in RF-CBT: *validation of patient experience by psychoeducation that normalises and explains RNT; validation of patient experience by therapist; learning self-compassion skills*).
4. Improving attentional focus to present-moment experience, with evidence that mindfulness and task absorption counteract RNT^{8,31,32} (corresponding component(s) in RF-CBT: *absorption in direct experience; attentional training*).
5. Generating explanations for symptoms and difficulties, which reduces the search for understanding, insight and certainty shown to drive RNT^{13,14} (corresponding component(s) in RF-CBT: *individualised rationale, psychoeducation, therapist empathy and understanding*).

We note that some of these elements are shared with general CBT and are not specific to RF-CBT but that each is a component in the overall RF-CBT package that has the strongest evidence for effectively reducing RNT. There is both good empirical evidence and strong theoretical rationales to support each of these hypothesized mechanisms.

The proposed research will advance knowledge in relation to:

- (a) How the change in RNT plays a causal role in the resolution and prevention of mental health problems, by examining the effects of manipulating RNT via components of RF-CBT and by examining reduction of RNT, assessed in multiple ways (self-report, EMA) as a short and long-term mediator of reductions in anxiety and depression.

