8.5. Follow up data collection

8.5.1. Weekly micro-assessments (during the intervention stage)

At week 1, 2, 3, 4, 5, 7, 9, 11, 13, 15, participants will receive prompts to complete brief questionnaires (micro-assessments) via the mPath App. The schedule for these questionnaires will start from the day the participant reinstalls mPath with their second invitation code, provided to them at the point of randomisation. The questionnaires collected during the micro-assessments will include condensed (2-3 item versions) of self-report and brief problem description measures of mediators, as well as brief outcome measures of RNT, anxiety (GAD2), depression (PHQ2), as detailed in Table 3. Participants will also be prompted to complete two brief questions in weeks that the full micro-assessment is not required (weeks 6, 8, 10, 12 and 14). This is to maintain engagement and to keep m-Path live on their phones (i.e., prevent the App from being put to sleep by the operating system).

Participants will have a +4 day window each week to complete the micro-assessments, after which the assessment will no longer be accessible to the participant. If any of the micro-assessments or engagement prompts are not completed, the participant will be sent an email to increase their engagement with the app and reminding them to open the m-Path app to ensure future survey notifications are received (i.e. to avoid the app going into sleep mode).

During the intervention period we will also collect data on engagement with the intervention (see Section 9 for more details).

8.5.2. 16 weeks post-randomisation

At 16-weeks post randomisation, participants will receive an automated SMS text message and an email with a link to complete the follow up questionnaires as surveys via REDCap Academic. On week 16 participants will also be invited to complete EMA for another 10-14 days (see the EMA thresholds under the Baseline Section 8.3) via the m-Path App. The schedule for the EMA will start from the day the participant reinstalls mPath with their second invitation code, provided to them at the point of randomisation. The questionnaires and data collected at 16 weeks post-randomisation are detailed in Table 3.

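### Linguistic indices scored from text written inside the treatment platform, if used as mediators, mix response to the allocated exercises with change in the mechanism

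*Protocol*

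**What the plan says.** Section 3.3.3 of the Protocol, headed as process measures (putative mediators), contains two linguistic measures.

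- The first rests on tasks set within the assessments: "Linguistic analysis of instructed writing tasks (e.g., asking participants to describe a problem; describe an example of RNT) at baseline and 16 weeks follow-up".
- The second has its own bullet: "Linguistic analysis of text generated during the intervention – as above". The text before it makes this conditional on viability and gives its purpose: "we will apply this linguistic analysis to the text provided within the exercises and open text boxes in the treatment platform". The hoped-for uses are insight into therapeutic process and to "track session-by-session change in these indices and test if these linguistic indices predict outcomes".

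Section 3.2, item 5, names both sources of text, the assessments and the online package. It treats both as carrying markers of change in the relevant mechanisms, without distinguishing them. It adds a possible further use: "We will explore whether these markers can be provided in real-time in order to provide ongoing feedback to participants within the intervention".

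The platform content is what is randomised. There are 16 variants (Study Summary), components are interleaved through the whole course (4.1), and each participant can open only the allocated variant (8.4). The Rationale describes the component behind Be Specific as "increasing specific contextualised detail in description of events and plans"; the component behind Be Kind includes learning self-compassion skills.

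Text is also collected outside the treatment exercises during therapy: the m-Path micro-assessments include "brief problem description measures of mediators" (8.5.1).

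**The concern.** A mediator has to be measured in the same way at both levels of the factor whose effect it is meant to carry. Exercise text may not meet that condition. A participant at the high level of Be Specific who does the exercise as taught will tend to write more concrete text in that exercise. The same holds for Be Kind and self-compassionate language. A difference in the index between levels could then appear even if nothing changed in how the person thinks outside the exercise.

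What is at stake is how these indices would be read. A component-to-index difference could be reported as the component engaging its mechanism, and could supply the first step of a mediation claim, when part of it reflects the task. Two of the four mechanisms are exposed: abstract-to-concrete processing and self-compassion, the two for which 3.3.3 offers linguistic analysis as a behavioural index.

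**Working it through.** **1. Are treatment and instrument separate?**

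| Text source | Where written | Differs by variant? | Pre-randomisation baseline? |
|---|---|---|---|
| Instructed writing tasks (3.3.3, Table 3) | Baseline and 16-week assessments | No variation described | Yes |
| Problem description in micro-assessments (8.5.1) | m-Path, one schedule for all | No variation described | Not listed at baseline in Table 3 |
| Exercises and open text boxes (3.3.3) | MyDataHelps, inside the allocated variant | Inferred from the component descriptions | No: access follows randomisation (8.4) |

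Only the third source sits inside the manipulated content. The index scores how abstract or specific the text is, and Be Specific works on the specificity of descriptions. Self-compassion overlaps with Be Kind in the same way. Because access opens only after allocation, even the first text entered may already reflect the variant, so adjustment for a baseline value is not possible. The protocol names no text box common to all variants and no rule for separating response to an exercise from change in processing.

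**2. The plan's own figures.** Section 13.1 gives d = 0.20, 90% power, alpha 0.05 (two-sided assumed), N = 1054 and about 2192 after 52% dropout.

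- Per level: n = 2(1.960 + 1.282)²/0.20² ≈ 526, or 1052 in total (stated 1054). Power at 527 per level is 0.901.
- Inflation: 1054/(1 − 0.52) = 2196 (stated 2192).

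Both agree closely. The point does not depend on them; 1054 is used below only as a realistic analysed sample.

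**3. Illustration of the joint significance test (section 5).** These assumptions are not in the documents:

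- the component leaves the mechanism T unchanged and lowers RNT directly by 0.20 SD;
- the index is (T + noise)/√2 plus a prompt shift of 0, 0.2 or 0.5 SD at the high level;
- T correlates with RNT at 0, 0.1 or 0.2 in absolute value.

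There were 2000 simulated trials per setting.

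| Prompt shift (SD) | Component-to-index path significant | Mediation declared, correlation 0 | Correlation 0.1 | Correlation 0.2 |
|---|---|---|---|---|
| 0 | about 5% | 0.4% | 3% | 6% |
| 0.2 | about 90% | 5% | 55% | 90% |
| 0.5 | 100% | 5% | 63% | 100% |

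Hand check at a shift of 0.2:

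- First path: z = 0.20 × √(527/2) = 3.25, so power ≈ Φ(3.25 − 1.96) = 0.90.
- Second path at correlation 0.1: the index-RNT correlation is 0.1/√2 = 0.071, so z ≈ 0.071 × √1054 = 2.30 and power ≈ Φ(0.34) = 0.63.
- Product: 0.90 × 0.63 = 0.57, against 0.55 simulated.

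A prompt effect therefore makes the first path uninformative. False mediation follows only when writing style is also related to RNT; with no such relation the rate is about 5%. Since z for a fixed shift grows with the square root of N, a larger sample does not remove the problem.

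**The case against.** The strongest reply is that this is a conditional, exploratory sub-analysis and that the main mediation work lies elsewhere. Much of that stands.

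- The platform-text analysis depends on viability, and its stated aims are process insight, tracking and prediction of outcome. Tracking within a person, or prediction among people on the same variant, need not be biased by prompt differences between levels.
- Table 1 (3.3.5) lists no linguistic measure among the process mechanisms for the primary objective. Tables 1 and 3 schedule linguistic analysis at baseline and 16 weeks only.
- Sections 3.3.3 and 13.3.3 assign mediation over time to the micro-assessments, which are collected outside the treatment platform. Both exposed mechanisms also have questionnaire measures.
- Exercise wording is not shown, and all variants share core content (4.1). How far the prompts differ is an inference.
- Section 13.3.3 leaves full specification of secondary analyses to the SAP, which was not available.

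This narrows the point but does not remove it. The separate bullet stands under a putative-mediators heading, and 3.2, item 5, reads both text sources as evidence of mechanism change. A SAP that followed those two statements would carry the mixing forward.

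A reader might also infer that real-time feedback of the markers will train specificity and self-compassion at the low levels during the trial. The documents do not support that. Section 3.2 only says the possibility will be explored, the intervention description contains no such feature, and section 17.10 sends changes that may affect intervention content to the TMG and TSC for review before implementation.

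**Conclusion.** The concern holds in limited form. If in-platform text is used as a mediator, or to show that a component engages its mechanism, between-level differences in the linguistic indices for Be Specific and Be Kind cannot be attributed to the mechanism. They combine response to the exercise and real change, and the documents give no means of apportioning the two. The size cannot be computed from the protocol; the simulated percentages rest on assumed prompt shifts and correlations and show only what could happen.

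Two stronger readings should be resisted. One is that these indices record the exercise and nothing of the mechanism; the documents support a mixture, not an absence of signal. The other is that the trial's answer to its primary objective is compromised. The primary outcome, the sample size, the instructed writing tasks and the micro-assessment mediation analysis do not depend on exercise text. The conclusion assumes that prompts or task content differ between variants in the way the component descriptions imply; if a given text box is worded identically for everyone, the objection to different prompts does not apply to it.

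**What to change.** In 3.3.3 and 3.2, item 5, state that linguistic tests of component-to-mechanism effects and of mediation use only text from prompts worded identically in all 16 variants: the baseline and 16-week writing tasks, the micro-assessment problem descriptions, and any text box in the common core content. State that text from component-specific exercises serves only as an engagement or manipulation check, or for description within variant. Bring the linguistic rows of Tables 1 and 3 into line with whichever text sources are kept, since they now show only baseline and 16 weeks.

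The cost is a wording change in the protocol, carried into the SAP. No new data are needed, because assessment and micro-assessment text is already collected. The downside is less text per person for linguistic mediation.
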